We subsequently performed several studies which suggest that spinal release of oxytocin represents the protective factor against chronic pain after childbirth. Intrathecal injection of the specific oxytocin receptor antagonist, atosiban, temporarily reverses the blockade of nerve injury induced hypersensitivity in the postpartum period in rats. Similarly, intracerebroventricular administration of the α -adrenoceptor antagonist, phentolamine, which is known to block the effects of lactation on activation of oxytocin-containing neurons in the paraventricular nucleus (PVN) of the hypothalamus, also temporarily reverses the blockade of nerve injury induced hypersensitivity in the postpartum period in rats. Finally, protection against hypersensitivity from nerve injury is abruptly reversed when pups are separated from dams for 24 hr, and this is accompanied by a large decrease in oxytocin concentration in cerebrospinal fluid. Although we are currently performing more clinical and laboratory studies to further define this mechanism, these data suggest that spinal oxytocin receptor stimulation in the period immediately following delivery protects against the generation of injury-induced hypersensitivity and subsequent chronic pain.

We recently completed a Phase 1 safety study of intrathecal oxytocin and observed no serious adverse events over the dose range studied (5-150 μ g). One subject at the 150 μ g dose had transient subjective numbness in sacral dermatomes, but this was preceded by a vasovagal episode beginning just prior to spinal injection, and this did not occur in other subjects at this dose. There were no objective signs of motor or sensory dysfunction in any volunteer, and blood pressure, heart rate, sensorium, corrected QT interval and serum sodium were unaffected.

We anticipate that oxytocin will be effective after spinal injection in humans against chemical induced hypersensitivity states. For these future studies, we will use a controlled and blinded study of intrathecal oxytocin against topical capsaicin, which we have used in previous studies under IND of spinal analgesics and which results in an area of increased pain sensation to a normally painful stimulus (hyperalgesia) and pain sensation to what previously was an innocuous stimulus (allodynia). This model of superficial and deep neuropathic pain in humans can be easily studied in volunteers, as these sensations last only a few hours and are not

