METHODS: Equal numbers of healthy men and women will be recruited. At least 3 days prior to study subjects will be trained to rate pain in response to heat applied to the lateral calf using a Peltier controlled thermode, and to rate pain in response to 225 mN von Frey filament testing within the area of hypersensitivity induced and maintained by transient application of topical capsaicin followed by intermittent heat (Petersen, 1999).

Subjects will return for study visit two and be randomized into one of 3 groups of 12 subjects each to receive, in a double-blind manner, intrathecal saline or intrathecal oxytocin, 15 µg or 150 µg. The solutions will be prepared and dispensed to this institution under IND approval and regulation from the Food and Drug Administration and will be released to the investigators through the research pharmacy at Wake Forest School of Medicine.

A stimulus response to heat pain will be performed, then intrathecal injection of the study solution in a 3 ml volume will occur via a #27 or #25 Whitacre needle inserted in a lower lumbar interspace. Thirty minutes later capsaicin will be applied to the lateral calf to generate hypersensitivity. Capsaicin will be removed and the area re-kindled 40 min later by application of a thermode at 40°C for 5 minutes. Areas of hyperalgesia and allodynia and, within the area of hyperalgesia, stimulus response to von Frey filament testing, will be determined upon removal of capsaicin and after 3 rekindlings at 40 minute intervals.

We will abandon an individual participant's study and schedule another participant to receive the same randomization, should we be unable to successfully place the intravenous catheter (IV) or the spinal needle to inject the intrathecal oxytocin. In our experience, this occurs in less than 10% of participants. We maintain an extensive listing (IRB approved Database BG 05-468: PI: [name].) of our previous Clinical Research Unit (CRU) volunteers who have requested to be notified by mail or email that they might qualify for participation in another volunteer study. It is from this list and potential volunteers that we maintain that we

anticipate recruitment of most of our volunteers. Should we need to advertise for additional volunteers we will submit a proposed advertising method to the IRB for approval.

STUDY DESIGN

Inclusion Criteria: We request permission to study up to 40 subjects so that we will have 36 evaluable subjects.

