A monitor tracing from the EKG will be recorded at 15 minute intervals for the first hour then hourly until discharge. If either BP or HR change by > 30%, or oxyhemoglobin saturation decreases to less than 90, and require treatment, these vital signs will be repeated at 5-minute intervals until vital signs are stabilized. A screening neurologic exam along with questioning for qualitative symptoms will be performed at 45, 90, 150, 210, 240 minutes, and 24 hours. The screening neurologic test will consist of examining both an arm and leg for deep tendon reflexes (DTR's), light touch, extension/withdrawal strength. In addition we will ask the volunteer about

other symptoms to include sedation, anxiety, nausea, GI, bladder, dizziness, extremity weakness, or any other symptom which was not specifically asked. Any symptom proffered will be categorized on a scale of the volunteer's choosing.

Treatment of Side Effects: Mean blood pressure elevations greater than 30% of baseline will be treated with labetalol 5-15 mg IV incrementally until BP elevation is less than 30% elevated. If BP elevation is judged to be due to pain following spinal oxytocin injection, we will treat pain first (at the volunteer's request) and only treat BP elevations if the volunteer has sufficient analgesia (he does not desire additional analgesia). Reductions in mean BP > 30% of baseline will be treated with incremental ephedrine 5-20 mg, IV. Heart rate (HR) reductions or elevations > 30% of baseline will be treated with incremental glycopyrrolate 0.2 mg IV or propranolol 0.2 mg IV, respectively. Peripheral oxyhemoglobin desaturation (< 90) will be treated with supplemental oxygen, nasal cannula, face mask, or non-rebreathing mask depending upon the degree desaturation and the response to therapy.

Completion of Day 2 Assessment

1. Vital signs are within normal limits blood pressure (systolic 90-140 mmHg; diastolic 50-90 mmHg) resting heart rate 45-100 beats per minute) without medication
2. He or she can ambulate without difficulty (no motor, balance affects).
3. Someone other than the volunteer will take the volunteer home (requirement for participation).
4. Volunteer promises to stay home where he or she can be contacted by telephone (requirement for participation).

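### The study-day symptom list does not name numbness, so a repeat of the Phase 1 sacral numbness at 150 µg would be caught only by open or general questions, not by a direct item asked alike in every arm

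*Combined protocol and SAP*

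**What the plan says.** **Phase 1 (Background).** Over a dose range of 5 to 150 µg, one subject at 150 µg had "transient subjective numbness in sacral dermatomes, but this was preceded by a vasovagal episode beginning just prior to spinal injection". The text adds that "this did not occur in other subjects at this dose" and that "There were no objective signs of motor or sensory dysfunction in any volunteer". It does not give the number treated at 150 µg, or when the numbness began and ended.

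**This trial (Methods).** Subjects will "be randomized into one of 3 groups of 12 subjects each to receive, in a double-blind manner, intrathecal saline or intrathecal oxytocin" at 15 µg or 150 µg. So 12 volunteers receive the dose at which the event was seen, and 12 receive saline through the same spinal procedure.

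**Study-day ascertainment (Safety and Monitoring, Assessment of Side Effects).** A screening neurologic exam with symptom questioning "will be performed at 45, 90, 150, 210, 240 minutes, and 24 hours". The exam consists of "examining both an arm and leg for deep tendon reflexes (DTR's), light touch, extension/withdrawal strength". Volunteers are also asked about "other symptoms to include sedation, anxiety, nausea, GI, bladder, dizziness, extremity weakness, or any other symptom which was not specifically asked". Symptoms they report are graded on a scale that the volunteer chooses.

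**Later contacts.** After discharge, the research nurse calls at 6 and 12 hours with a general question about problems. Long-term Follow-up has contacts daily for 5 days, weekly for 1 month and at 6 months, with questions about neurologic symptoms as a class, spinal headache and other complaints. The Risks section describes the same follow-up schedule as asking about local discomfort or headache.

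**Analysis.** The Statistical Rationale covers only the area of hyperalgesia. It gives no tabulation of symptoms by arm.

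**The concern.** The sponsor documents one neurologic symptom from its own Phase 1 study, at a dose used again here, and the list of named symptoms omits it. Of the seven items, extremity weakness is motor and bladder is a different function, so neither stands in for numbness.

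The Phase 1 event was felt by the subject and left no objective sign. Direct questioning is therefore the check best suited to finding a repeat, and it is the check that lacks the item.

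What is at stake is the quality of the comparison. Phase 1 left open whether the numbness came from the drug, the spinal procedure or the vasovagal episode. A randomized, double-blind trial with a saline arm is the natural place to look at that, because every arm undergoes the same procedure. If the seven named symptoms are asked for directly while numbness depends on an open question, numbness will probably be less completely reported than the rest. A low or zero count at 150 µg could then be given more weight than it deserves.

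**Working it through.** No figure in the plan bears on this point, so there is none to reproduce. The check sets the Phase 1 event against each means of detecting it, then illustrates the scale.

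**Step 1: would each planned contact pick up a subjective sacral numbness?**

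| Contact | What is asked or tested | Numbness named? |
|---|---|---|
| 45, 90, 150, 210, 240 min, 24 h: questions | Seven named symptoms, then an open item | No; open item only |
| Same times: exam | Reflexes, light touch and strength on an arm and a leg | Active sensory test, but the Phase 1 event had no objective signs |
| 6 h and 12 h calls | General question about problems | No |
| Daily for 5 days, weekly for 1 month, 6 months | Neurologic symptoms as a class | No; general, and by recall |

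Reporting is invited at every contact, but at none is numbness asked for by name.

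**Step 2: what can zero cases in 12 show, even with complete reporting?** The one-sided 95% upper bound solves (1 − p)^12 = 0.05:

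1 − 0.05^(1/12) = 0.221, about 22%.

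The upper limit of the two-sided 95% interval is 1 − 0.025^(1/12) = 0.265, about 26%.

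**Step 3: illustration of incomplete reporting.** Let p be the true rate of transient numbness at 150 µg and s the share of cases that get reported. The documents give neither, so both are assumptions. The chance of at least one recorded case in 12 is 1 − (1 − p·s)^12.

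| Assumed p | s = 1 | s = 0.5 | s = 0.25 |
|---|---|---|---|
| 5% | 0.46 | 0.26 | 0.14 |
| 10% | 0.72 | 0.46 | 0.26 |
| 20% | 0.93 | 0.72 | 0.46 |

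For p = 10%: 1 − 0.90^12 = 0.718; 1 − 0.95^12 = 0.460; 1 − 0.975^12 = 0.262. The column s = 1 is a ceiling, since a direct question need not capture every case. The table shows direction and rough scale; it does not estimate what this trial will lose.

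**Step 4: can the arms be compared formally?** At p = 10%, 12 × 0.10 = 1.2 cases are expected at 150 µg. Against 0/12 on saline, the two-sided Fisher exact p-value is 2 × C(12,4)/C(24,4) = 2 × 495/10,626 = 0.093 for 4/12, and 2 × C(12,5)/C(24,5) = 2 × 792/42,504 = 0.037 for 5/12. At least five cases would be needed for p < 0.05, so the tabulation would be descriptive.

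**The case against.** The strongest reply is that a short checklist with an open question is a legitimate way to elicit symptoms, that nothing in the documents contradicts it, and that 12 per arm cannot settle a rare symptom however it is asked. The last part stands: Steps 2 and 4 show that a zero would not be reassuring and that only a large excess would separate the arms. Prompting would also raise reports in every arm. The first part stands as a defense of the method, but it does not explain why the one neurologic symptom reported from Phase 1 is missing from a list that names seven others.

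Several stronger readings are tempting and should not be drawn:

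- *Numbness is recorded only if the volunteer raises it.* This is not so. The open question is put at six time points, the 6- and 12-hour calls invite any problem, and Long-term Follow-up asks about neurologic symptoms.
- *Phase 1 showed a drug effect at 150 µg.* The documents describe one subject, a vasovagal episode that began before the injection, and no such event in others at that dose.
- *The exam fails because no sacral site is named.* A symptom without objective signs would not be expected to show on light touch, wherever it is tested.
- *An early event is missed because questioning starts at 45 minutes.* The onset and duration of the Phase 1 event are not given, and a volunteer asked at 45 minutes may well recall it.
- *Numbness would shrink the mapped area of hyperalgesia.* Mapping is on the lateral calf, and nothing in the documents links subjective sacral numbness to sensation there.

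**Conclusion.** The point holds in a narrow form. The study-day list names seven symptoms but neither numbness nor tingling, although the Background reports such an event at a dose that 12 volunteers will receive. A repeat would be detected through open or general questions only, not through a direct item asked the same way in each arm.

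The gap follows from the text alone. Its effect cannot be measured from the documents. Under assumed true rates of 5% to 20%, a fall from full to half reporting lowers the chance of recording at least one case in 12 from 0.46 to 0.26 at the low end and from 0.93 to 0.72 at the high end. The true rate and both reporting shares are assumptions. This is an inexpensive improvement to how a known symptom is ascertained, and it affects neither the primary endpoint nor the sample size.

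**What to change.** In Safety and Monitoring, Assessment of Side Effects, add *numbness or tingling in the legs, buttocks or saddle area* to the symptoms asked about by name. Ask it in the same words in all three arms at the existing questioning times, and keep the open question. State that the number of volunteers reporting it will be tabulated by arm, as a description and without a test.

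Optionally, ask the same question at the 15- and 30-minute vital-sign checks, when staff are already with the volunteer. The case for this is weaker, because the onset time of the Phase 1 event is not given.

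The cost is one line on the symptom form and one row in a table, plus two brief questions if the optional times are used. The main downside is more reports of numbness in every arm, including saline, so the count should be read against saline and not alone. A zero at 150 µg should be reported with its upper bound of about 22%.

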We will instruct the volunteer to call us, providing beeper and telephone numbers of the research nurse and the investigators should he have any questions or problems. The research nurse will call the volunteer at 6 hours and 12 hours post-spinal oxytocin injection inquiring about any perceived problems.

Study Visit 3: Approximately 24 hours after the spinal oxytocin injection the subject will report to the CRU to have a blood sample drawn for a Basic Metabolic Panel to assess serum sodium levels.

RISKS

Risks of spinal needle insertion include pain on insertion, local bruising or soreness, post-dural puncture headache, and permanent nerve injury. Participants in this study will be informed regarding these risks. Local anesthesia will be used to prevent pain on needle insertion, and a small (#25 or #27) Whitacre tip needle used to minimize local trauma and risk of headache. We routinely telephone all volunteers daily for 5 days. Participants will also be contacted weekly for 1 month, then approximately 6 months after the study to inquire regarding local discomfort or headache. There is a risk (less than 1%) of developing a headache from the spinal needles. If a subject develops a headache that does not go away and is bothersome, offer to perform an epidural blood patch. This procedure is 95% effective in treating the headache. Rarely (5 out of 100 times) is a 2nd blood patch needed. Other risks of the epidural blood patch are the same as the spinal. The risk of paralysis, infection or nerve damage from a spinal procedure is extremely rare, less than one chance in 20,000. The numbing medicine that we put under your skin right before the spinal needle is inserted may cause you to have a brief period (about 5 seconds) of mild discomfort. We have had no local discomfort lasting more than 2 weeks and only 1 headache in 438 subjects that required epidural blood patch treatment.

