This Phase II trial will be performed with a data safety monitoring committee ([name] and [name].) who is not involved in the study. Data and adverse events will be reported to these individuals quarterly. Adverse events will also be reported to the IRB and the FDA (since trials are being conducted under an IND). Serious adverse events will be reported to all of these groups and the data safety monitoring individuals within 24 hr and the trials halted until feedback is obtained from each. Data and any adverse events will be monitored and reviewed by the PI after treatment of each subject.

Minority, Gender, and Children Participation

Based on previous experience with volunteer studies, women will represent 40-60% of participants in the proposed studies. However, as seen in the table below from the past cycle with volunteers, it is unlikely that more than 20% of participants will be minorities. There is no reason to suspect a difference among races in response to these analgesic compounds, so from a scientific viewpoint this will not be detrimental. We will recruit from our IRB approved Database (BG 05-468). Children under age 18 are not included in these protocols because this protocol involves the use of experimental compounds and we believe they should be first characterized in adults. Furthermore, the study of experimental pain in children volunteers is

difficult ethically. For these reasons we anticipate studying approximately 6-7% of our subjects under age 21, and none under age 18.

Volunteer Payment

Participants will be paid a total of \$500. We believe that this payment schedule is fair and appropriate, paying for each procedure attempted and an additional payment for completion of the entire study.

Placement of IV: \$25

If IV placement unsuccessful, the volunteer is paid and the study abandoned.

Placement of Spinal: \$125 and study drug administration

If the 1st spinal is attempted but proves unsuccessful, the volunteer is paid \$100 and the study abandoned,

Application of capsaicin cream: \$25 for each application (total \$50)

Completion of entire study: \$300

Volunteer must complete all of the above phases to receive this payment.

Long-term Follow-up

Volunteers will be contacted daily for 5 days, weekly for 1 month, and at 6 months after the study and questioned about neurologic symptoms, symptoms of post-dural puncture headache (spinal headache) or other complaints.

STATISTICAL RATIONALE

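### Reported symptoms are graded on whatever scale each volunteer picks, so symptom severity cannot be described by dose group

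*Combined protocol and SAP*

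**What the plan says.** The combined protocol and SAP deals with reported symptoms under Safety and Monitoring, in the part on assessment of side effects. The timing is explicit: "A screening neurologic exam along with questioning for qualitative symptoms will be performed at 45, 90, 150, 210, 240 minutes, and 24 hours". Seven prompts are listed (sedation, anxiety, nausea, GI, bladder, dizziness, extremity weakness), followed by anything not specifically asked about. The grading rule is one sentence: "Any symptom proffered will be categorized on a scale of the volunteer's choosing".

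METHODS makes this a parallel-group trial: subjects will "be randomized into one of 3 groups of 12 subjects each to receive, in a double-blind manner, intrathecal saline or intrathecal oxytocin", at 15 µg or 150 µg.

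The only fixed thresholds for a side effect, in the same safety section, concern mean arterial pressure, heart rate and oxygen saturation. STATISTICAL RATIONALE specifies one group comparison, a one-way ANOVA on area of hyperalgesia. It contains no safety analysis.

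**The concern.** A self-chosen scale can show whether one person is getting better or worse, provided that person keeps to it. It does not allow one person to be compared with another. In a parallel-group trial, any description of severity by dose compares different people, so it needs a shared metric.

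This is more than a detail left to the case report form. The plan states a method, and following it as written produces grades without a common unit. What is at stake is a dose-by-severity description of symptoms that neither meet the vital-sign thresholds nor count as serious. RISKS says that the exact risks of the drug are not known and promises to monitor how sleepy subjects become. That is a graded quantity for which the plan provides no common grade.

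**Working it through.** The plan states no figure to reproduce, and the point depends on no variance, effect size or power. The check is a reading of the relevant sections side by side.

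1. **Is a common scale given elsewhere?** No.
   - Safety and Monitoring defines significant side effects by vital signs only. Its reporting rule turns on whether an event is unexpected or serious.
   - Data Safety Monitoring Plan turns on seriousness and mentions no severity grade.
   - Completion of Day 2 Assessment has an ambulation check and telephone calls, but no symptom scale.
   - Long-term Follow-up asks about symptoms and names no scale.
   - STATISTICAL RATIONALE does not mention symptoms.

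2. **Does another reading of the sentence remove the problem?**
   - *Proffered* may cover only symptoms raised without a prompt. The seven prompted symptoms then have no stated scale at all.
   - The sentence may mean that the volunteer, not the staff, picks the category. The categories are still not stated.
   - The text says *scale* and does not use the word severity. A severity grade is the natural reading, but it is a reading.

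3. **What follows for the data?** Suppose one volunteer answers in words (mild, moderate, severe) and another on 0 to 10. The plan gives no rule for putting the two on one axis. Later rescaling would be partial at best, and possible only if each volunteer's end-points were recorded, which the plan does not require.

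4. **How many occasions are involved?** Six questionings × 12 participants = 72 per group, and 72 × 3 = 216 in all, if every participant completes every time. This is the number of occasions on which a grade *could* be recorded. The number of grades depends on how often symptoms occur, and the documents give no rate.

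5. **What is unaffected?** Whether and when a symptom was reported, vital signs, the neurologic examination, serious events, treated side effects, the discharge ambulation check and 24-hour sodium can all be described by group. None depends on the self-chosen scale. The ANOVA on area of hyperalgesia and its power calculation do not use symptom data.

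**The case against.** The strongest case on the other side is that the plan does not set out to measure symptom severity. It calls the exercise questioning for qualitative symptoms, its goal concerns hyperalgesia and allodynia, the investigator reviews each subject individually, and no symptom comparison is planned. With 12 per group, even a common scale would support description only. This stands, and it limits the point to a minor one. It does not remove it, because the plan does direct that a scale be used and the scale it directs cannot serve a description by dose.

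Four stronger readings are tempting, and the documents do not support them.

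- **Bias between groups.** A reader might infer that severity would be distorted by arm. Allocation is randomized and double-blind, and nothing in the documents suggests that choice of scale would differ systematically by group. The choice may be made after dosing, so this is not absolute, but the main cost is noise between people.
- **Later contacts.** A reader might extend the problem to the telephone calls ("The research nurse will call the volunteer at 6 hours and 12 hours post-spinal oxytocin injection inquiring about any perceived problems") and to long-term follow-up. The self-chosen scale is not stated for these contacts. They simply lack form detail, which is a separate and weaker matter.
- **The Phase 1 case.** BACKGROUND reports one subject at 150 µg with "transient subjective numbness in sacral dermatomes, but this was preceded by a vasovagal episode beginning just prior to spinal injection", and adds: "There were no objective signs of motor or sensory dysfunction in any volunteer". A reader might take this as proof that ungraded symptoms get missed. It shows the opposite for detection: the symptom was caught because the subject reported it, and this trial will also ask.
- **The safety committee.** The plan says: "Data and adverse events will be reported to these individuals quarterly". A reader might infer that the committee would receive incomparable grades. The plan does not say that those reports contain severity grades, so this would be conjecture.

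**Conclusion.** The point holds as a small, cheap improvement to descriptive safety reporting. For the six scheduled questionings, the plan prescribes a grading method that yields no common metric across volunteers, so symptom severity cannot be described for saline, 15 µg and 150 µg.

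The conclusion rests on two assumptions: that the sentence refers to grading of severity, and that no common scale sits in a form outside these documents. Its practical size cannot be fixed without a symptom rate. If few symptoms are reported, little is lost. It is no reason to doubt the primary analysis, the power calculation or the rules for serious events and vital signs.

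**What to change.** Replace the sentence with one common ordinal scale, for example none/mild/moderate/severe, applied to every prompted and every volunteered symptom at the six scheduled times. Keep a free-text line for the volunteer's own words. Tabulate the worst grade per participant by group, descriptively and without a test. Using the same scale at the later follow-up contacts would be a sensible option, but the point does not depend on it.

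The cost, in my judgment, is one sentence in the protocol and a grading column on the form used at times already scheduled, with no added visits or calls. The downside is slightly less freedom for volunteers to describe symptoms in their own terms, which the free-text line largely keeps. No dose, treatment threshold or other clinical rule changes.
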